### 2.1. Study Design

*This is a Phase 2b, multicenter, parallel-group, placebo-controlled, randomized, double-blind study to evaluate Staphylococcus aureus 4-antigen vaccine (SA4Ag) safety and efficacy in the prevention of postoperative S aureus disease in adults aged 18 to <86 years who are undergoing elective open posterior instrumented spinal fusion procedures with multilevel instrumentation.*

This is an event-driven study with a total target of 48 primary endpoint *S aureus* cases; it is anticipated that approximately 6,000 subjects will be enrolled globally to accumulate these 48 cases. However, the total enrollment number may vary based on the incidence rate of the primary endpoint, true underlying vaccine efficacy (VE), and potential early study stop for efficacy or futility.

*There are 5 scheduled study visits and 1 scheduled telephone contact during 6 to 8 months of subject participation. Study-eligible subjects who provided consent will be randomized in a 1:1 ratio to receive a single dose of SA4Ag or placebo at Visit 1, which occurs 10 to 60 days prior to undergoing elective open posterior instrumented spinal fusion procedures with multilevel instrumentation (index surgical procedure). Visit 2 is a longitudinal visit and is to monitor the index hospital admission period from the day of surgery (Day 1) until the day of discharge. A telephone contact with the subject will occur on Day 21, while postoperative evaluation study visits will occur on Day 42, Day 90, and Day 180 after surgery.*

*Following the index hospital admission, unscheduled visits will be conducted for assessment of suspected bloodstream infection (BSI) and/or surgical-site infection (SSI) events, and to assess hospitalization(s) subsequent to the index hospital admission.*

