### **8.1.3.5. Immunogenicity**

On December 20, 2018, the STRIVE study met its pre-specified futility criteria at its Interim Analysis and ceased enrollment. The rationale for this change in immunogenicity testing and analysis is to focus efforts on improving our understanding of why the vaccine did not appear to prevent post-operative *S. aureus* infections. This analysis will replace all previously planned immunogenicity analyses.

The immunogenicity testing and analysis will focus on the four objectives listed below:

Primary objective:

1. To assess the association between CP5/8, ClfA, and MntC functional antibody levels and *S. aureus* infections among subjects within the STRIVE study, adjusting for demographics, health status, and surgical characteristics

Secondary objective:

2. To describe the CP5/8, ClfA, and MntC functional antibody levels among surgical subjects at selected time points by case and vaccination status

Exploratory objectives:

3. To compare the functional immune response to CP5/8, ClfA, and MntC among vaccinated surgical subjects without *S. aureus* infection with vaccinated healthy (non-surgical) subjects
4. To compare the functional immune response of CP5/8, ClfA, and MntC at unscheduled BSI/SSI visit among subjects with *S. aureus* infection with scheduled visits of similar time intervals among subjects without *S. aureus* infection

Study Design:

A nested case-control study within the STRIVE study will be conducted to assess the association of *S. aureus* infection and immunogenicity endpoints at select timepoints, adjusting for demographics, health status, and surgical characteristics. Cases and controls will be matched by study site.

Cases will be any subjects (per protocol or mITT) with adjudication-confirmed *S. aureus*-related SSI and/or BSI (includes deep, organ/space and superficial SSIs). Infections with positive *S. aureus* cultures deemed not clinically significant by adjudicators will be excluded. Other invasive *S. aureus* infections will have descriptive analysis separate from objective 1 and without matched controls. At this time, there are 5 such cases: additional cases may be identified prior to study closeout.

Controls will be per protocol subjects from same study site as cases who completed Visit 5 (post-op Day 90) but did not develop adjudication-confirmed *S. aureus* infections. A total of 7 controls will be selected per case (5 vaccinated and 2 unvaccinated controls per case).

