At this time, the plan is to include a total of 51 cases of *S. aureus* infection (both SA4Ag vaccinated and placebo) and 357 controls will be included in this sub-analysis. For the few sites with a shortfall in available controls due to low enrollment, remaining controls will be randomly selected from other “case” sites (ie, sites with cases that have unselected controls remaining) to meet control targets. Extra controls will be associated with their actual site in the logistic regression analysis.

Data analysis:

All analyses will be performed for CP5/OPA, CP8/OPA, ClfA/cLIA, and MntC/cLIA.

*Objective 1:*

The key independent variables of interest are CP5 and CP8 functional antibody levels (as measured by OPA assay), and secondary independent variables include ClfA and MntC antibody levels (as measured by cLIA assay) assessed at the following time points.

The primary analysis will include the following immunogenicity variables (one value for each antigen for each specimen):

- Day of index surgery before surgery (V2 admission) log transformed titers
- V2 hospital discharge log transformed titers minus V2 admission log transformed titers [Quantify change from V2 admission]
- V5 post-op day 90 log transformed titers minus V2 hospital discharge log transformed titers [Quantify change from V2 discharge]

Multivariate conditional logistic regression will be conducted to model the odds of *S. aureus* infection based on functional antibody levels (ie, 3 immunogenicity variables based on V2 and V5 described above), adjusting for following covariates:

- Demographics (age, sex, race/ethnicity, BMI, ASA, CCI)
- Operative time (mins)
- Number of motion segments/intervertebral levels fused
- Proportion of blood loss (%)
- Units of transfusion
- Days from vaccination to surgery
- Days from surgery to discharge
- Primary versus revision spinal fusion surgery
- Season/year of surgery
- Colonization status (IHMA swab results)
- Diabetes
- Smoking status
- Intrawound antibiotic use (eg, vancomycin vs. other vs. none)

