It is recognized that this is an extensive list of potential covariates with a limited sample size. Model selection will attempt forward or backward selection approaches to arrive at a parsimonious model. Results will be reported as odds ratios (ORs) with corresponding 2-sided 95% CIs. Effect modification/interaction will be tested for select variables (eg, vaccination status, colonization status, blood loss, units of transfusion). Results of the multivariable conditional logistical regression will be reported as odds ratios (ORs) with 95% confidence intervals (CIs). Frequency counts and summary statistics (n, mean, standard deviation, median, minimum, and maximum) will be compiled for serology results and all covariates listed above by case/control status.

Proportion of blood loss will be estimated from blood loss (ml) divided by the estimated preoperative blood volume. Estimation of preoperative blood volume depends on sex:

- Male: volume (mL) =  $(0.006012 \times H^3)/(14.6 \times W) + 604$
- Female: volume (mL) =  $(0.005835 \times H^3)/(15 \times W) + 183$
- where H = height in inches and W = weight in pounds.

Additional sensitivity analyses include 1) repeating overall model for STRIVE primary endpoints only, 2) excluding controls with other non-*S. aureus* infections, and 3) limiting analysis to per protocol subjects.

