#### *Objective 2:*

Tabular summaries and graphical displays of serological results by case/control status and vaccination status at each sampling time point will be generated. The immunogenicity baseline will be the Visit 1 prevaccination blood draw. Assay values from sera obtained up to 7 days before vaccination will be considered eligible for analysis.

The number and proportion of subjects achieving threshold values will be obtained at each scheduled time point for vaccine group. Threshold values are identified in [Table 8](#). Two-sided 95% CIs will be compiled. Comparisons will be conducted by vaccination and case status (ie, placebo-case, placebo-noncase, SA4Ag-case, and SA4Ag-noncase) using the Fisher exact test, 2-sided.

Vaccine groups will be summarized by proportion of subjects achieving each of 4 thresholds simultaneously. The 4 antigens will be CP5/OPA, CP8/OPA, ClfA/cLIA, and MntC/cLIA. These proportions will be compiled for each scheduled visit. Two-sided 95% CIs will be compiled for each proportion. The vaccine groups will be compared using the Fisher exact test, 2-sided.

GMTs at select time points (V1, V2, V2 discharge, V5, and unscheduled BSI/SSI visits) are obtained by log transformations of indicated values, averaging the log values, then exponentiating the result. The associated 2-sided 95% CI will be obtained by calculating the CI in log scale, referencing the t-distribution, and then exponentiating the lower and upper limits.

GMFRs are geometric means of the titer from the indicated visit divided by the corresponding baseline titer. Subjects missing either baseline or the applicable visit titer are excluded from the calculation. GMTs, GMFRs, and their 2-sided 95% CIs will be calculated for each scheduled time point.

GMTs, GMFRs, and their associated 2-sided 95% CIs will be calculated again for each select time point, but the statistics will be obtained for vaccine group and case occurrence (yes/no), ie, placebo-case, placebo-noncase, SA4Ag-case, and SA4Ag-noncase. These time profiles will be compiled for BSI cases, SSI cases, and ISA cases. Subjects who have more than 1 type of case will appear in as many case categories as relevant. Profiles will be calculated for all time points up to 90 days. Titers obtained after case onset will be excluded, so sample sizes for cases will shrink over time.

GMTs and GMFRs will also be obtained for the following subjects with unscheduled BSI/SSI visits:

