- Subjects with any postoperative *S aureus* BSI and/or deep incisional or organ/space SSI occurring within 90 days of the index surgery, limited to unscheduled blood draws within 90 days
- Subjects with any postoperative *S aureus* BSI and/or deep incisional or organ/space SSI occurring within 180 days of the index surgery, limited to unscheduled blood draws within 180 days
- Subjects with any postoperative *S aureus* SSI within 90 days of the index surgery, limited to unscheduled blood draws within 90 days
- Subjects with any postoperative *S aureus* SSI within 180 days of the index surgery, limited to unscheduled blood draws within 180 days
- Subjects with any adjudicated postoperative ISA disease within 90 days of the index surgery, limited to unscheduled blood draws within 90 days
- Subjects with any adjudicated postoperative ISA disease within 180 days of the index surgery, limited to unscheduled blood draws within 180 days

Subjects with more than 1 endpoint of unplanned BSI/SSI assessment will participate in each relevant analysis.

If a specific unscheduled assessment visit was not done, serology samples collected at scheduled visits occurring within 7 days before or after the onset of a PDI may be used in these analyses.

Two additional analyses using ANCOVA will be performed to assess the association between absolute functional antibody levels (at V1 versus V2, V2 versus V2 discharge) and possible interfering host factors, include interaction terms.

1) *ANCOVA comparing V1 versus V2 admission*: This sub-analysis will be limited to those with serological testing at V1 which includes 51 cases and a subset of ~50 controls (chosen from among the 2 vaccinated controls per vaccinated case matched by site). Least-squares means (LSMs) and associated CIs for both vaccine groups at each postbaseline visit will be estimated from an analysis of covariance (ANCOVA). The dependent variable will be log V2 admission titer minus log day-of-vaccination (V1) titer. The model terms will be vaccine group, site, demographics (age, sex, race/ethnicity, BMI, ASA, CCI), colonization status at V1, diabetes, smoking status and elapsed number of days from V1 to V2 admission. Colonization status will be based on any *S aureus* at V1 and will be defined as positive if either nose or throat is positive; otherwise, it will be defined as negative.

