Type 3 sums of squares will be used. The difference between SA4Ag and placebo in LSMs will be obtained for V1 versus V2 admission. The exponentiated differences will be ratios of the vaccine groups' geometric means. The corresponding 2-sided 95% CIs will be obtained.

*ANCOVA comparing V2 admission versus V2 discharge*: An exploratory analysis of effect of blood loss on immunogenicity will be performed. This sub-analysis will include subjects with serological testing at both V2 admission and discharge which includes 51 cases and 357 controls. Loss of titer is assumed to be proportional to blood loss divided by the estimated preoperative blood volume. Assay titers will be log transformed. The dependent variable will be log day-of-discharge titer minus log day-of-surgery titer. If a subject has more than 1 set of relevant immunogenicity results after the index surgery, the earliest results will be used.

The statistical model will be ANCOVA. The model terms will be vaccine group, site, colonization status at V1/V2, , demographics (age, sex, race/ethnicity, BMI, ASA, CCI), diabetes, smoking status, elapsed number of days from the day of surgery to the day of discharge (calculated as the day of discharge minus the day of surgery, plus 1), proportion of blood loss (%), transfusion volume (mL), presence of specific types of transfusion (packed RBCs, platelets, whole blood and plasma), origin of blood product (heterologous or autologous, limited to subjects with packed RBCs or whole-blood transfusion), cell saver, case status and case status by vaccine group interaction. Colonization status will be based on any *S aureus* at V1 or V2 admission and will be defined as positive if either nose or throat is positive; otherwise, it will be defined as negative.

Other terms may be explored. Geometric means will be estimated for levels of statistically significant factors.

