**Table 26. Summary of Immunogenicity Analyses**

Endpoint	Populations	Statistical Method	Model/ Covariates/ Strata	Missing Data	Interpretation/Comments
Odds of S. aureus infection based on functional antibody levels at time points	mITT immunogenicity	Multivariable conditional logistic regression	The model terms will be demographics (age, sex, race/ethnicity, BMI, ASA, CCI), operative time (mins), number of motion segments/ intervertebral levels fused, proportion of blood loss (%) , units of transfusion, days from vaccination to surgery , days from surgery to discharge, primary versus revision spinal fusion surgery, season/year of surgery, colonization status, diabetes, smoking status, intrawound antibiotic use	N/A	Sensitivity analyses for primary endpoints only, excluding controls with other non- S. aureus infections, and limiting analysis to per protocol subjects.
Proportions of subjects achieving threshold at postvaccination time points	mITT immunogenicity	Fisher exact	Vaccine group	N/A	Describe immunogenicity

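### Objective 1 draws 5 vaccinated to 2 placebo controls per case but commits to no vaccine-group main effect, weight or offset, so sampling alone can make antibody look protective

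*SAP*

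**What the plan says.** The trial is "randomized in a 1:1 ratio to receive a single dose of SA4Ag or placebo at Visit 1" (SAP 2.1). After the futility stop, SAP 8.1.3.5 replaces all earlier immunogenicity plans with a nested case-control study of 51 cases and 357 controls. Each case, from either arm, gets the same control mix: "A total of 7 controls will be selected per case (5 vaccinated and 2 unvaccinated controls per case". Site is the only matching factor.

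Objective 1, labelled primary for this analysis, uses conditional logistic regression, and the SAP describes its outcome and exposures this way: "infection based on functional antibody levels (ie, 3 immunogenicity variables based on V2 and V5 described above), adjusting for following covariates". The list that follows covers demographics, surgery, transfusion, colonization and health status. Vaccine group is not on it, and no sampling weight or offset is mentioned. SAP Table 26 repeats the list, starting "The model terms will be demographics (age, sex, race/ethnicity, BMI, ASA, CCI), operative time (mins", again without vaccine group. None of the three sensitivity analyses adds it. The one reference in the Objective 1 modelling text is: "Effect modification/interaction will be tested for select variables (eg, vaccination status, colonization status, blood loss, units of transfusion". Covariates go through stepwise selection, and none is exempt.

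Elsewhere in the section, the admission-to-discharge ANCOVA on the same 51 cases and 357 controls lists vaccine group and ends with "cell saver, case status and case status by vaccine group interaction". Under Objective 2, for GMTs and GMFRs, "the statistics will be obtained for vaccine group and case occurrence (yes/no), ie, placebo-case, placebo-noncase, SA4Ag-case, and SA4Ag-noncase".

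**The concern.** Controls are selected on arm, at a ratio unrelated to the arm mix of the population that produced the cases. Arm is also the main determinant of titer: protocol 1.2.4 and 1.2.5 report robust responses to all four antigens by Day 15 to Day 29. Conditioning on site cannot remove the distortion, because the 5:2 ratio is intended within each matched set. If the vaccinated share of cases is below 5/7, controls have higher titers than cases by construction, and a model without arm reads this as protection. Above 5/7 the bias reverses.

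Objective 1 is the lead aim of an analysis meant to explain why the vaccine did not appear to work. A spurious finding that higher antibody protects would mislead exactly that question.

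**Working it through.** **1. Sampling arithmetic.** From SAP 8.1.3.5: 51 cases × 7 controls = 357, which reproduces the stated figure. Of these, 51 × 5 = 255 are vaccinated and 51 × 2 = 102 are placebo, so 255/357 = 71.4% are vaccinated.

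**2. Distortion of the vaccination odds ratio.** Let p be the vaccinated share of cases. With 1:1 allocation, SAP 8.1.1 gives VE = 1 − p/(1−p). In the sample, OR = [p/(1−p)] / (5/2).

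| p | Case odds | VE | Sampled OR | Apparent VE |
|---|---|---|---|---|
| 11/24 (futility boundary, SAP 8.1.1) | 0.846 | 15.4% | 0.338 | 66% |
| 0.50 | 1.0 | 0% | 0.40 | 60% |
| 0.60 | 1.5 | −50% | 0.60 | 40% |
| 5/7 | 2.5 | −150% | 1.00 | 0% |

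**3. Effect on titer.** I simulated 51 sets of 1 case, 5 vaccinated and 2 placebo controls, with 2,000 runs per cell and a conditional logistic likelihood. Titer had no effect on infection within either arm. Three titer variables were fitted, as planned: an admission titer that is N(0,1) plus a separation for vaccinated subjects, and two change scores unrelated to arm. Each cell gives the average OR per SD of admission titer, then the share of runs significantly protective (nominal 2.5%). There is no vaccine-group term.

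| Vaccinated share of cases | 0.5 SD | 1 SD | 2 SD | 3 SD |
|---|---|---|---|---|
| 11/24 | 0.89; 13% | 0.81; 35% | 0.77; 69% | 0.79; 82% |
| 50% | 0.90; 11% | 0.84; 23% | 0.81; 53% | 0.82; 69% |
| 60% | 0.95; 5% | 0.92; 9% | 0.89; 18% | 0.90; 23% |

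Variants:
- One titer alone, separations of 1 to 5 SD: 25% to 77% at a 50% share, 10% to 29% at 60%, and 1% to 3% at 5/7. At 65% (0.5 to 4 SD) it is 5% to 9%.
- Change scores that also differ by arm (assumed −0.15 × separation each, 1 to 5 SD): 21% to 45%, 9% to 17%, and 2% to 3% at 50%, 60% and 5/7.

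**4. Same runs with vaccine group added.** In all 12 cells of the table the titer OR is 0.995 to 1.005, the falsely protective rate is 2.0% to 3.2%, and the two-sided rejection rate is 4.0% to 5.7%.

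**5. Same runs with an offset.** A fixed offset of −ln(2.5) = −0.916 for vaccinated subjects gives OR 1.01 to 1.03 and two-sided rejection of 4.0% to 5.2% at a 50% share. It is approximate, because the ratio is fixed within each set. An offset of minus the log of the arm count in each set (case included), run with one titer, gives OR 1.00 and 2.1% to 3.0% falsely protective. At a 60% share the fixed offset gives OR 1.07 to 1.13: the arms then really differ in risk, and a cross-arm titer coefficient carries that difference.

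**6. What the documents suggest about the split.** The V1-to-V2 ANCOVA uses a "subset of ~50 controls (chosen from among the 2 vaccinated controls per vaccinated case matched by site". Read literally, 50/2 = 25 vaccinated cases, or 25/51 = 49%; the number is higher if the ~50 come from a larger pool. With the split fixed at 25/51 and one titer, the falsely protective rate is 24%, 60% and 94% at 1, 2 and 4 SD (1,000 runs). Using site strata of 3 cases and 21 controls instead of single-case sets gives 27%, 57% and 96% (100 runs).

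**The case against.** **Vaccination status is named for interaction testing, and such a test normally brings the main effect.** True, so it would be too strong to say that vaccination status is absent from the plan. But it is only an example, is missing from Table 26, can be dropped by selection, and does not adjust the reported main odds ratio.

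**The size rests on assumed inputs.** This stands. At a 50% share and 0.25 SD the falsely protective rate is only about 6%. The 49% reading is a floor and weak evidence, because the two vaccinated controls it refers to do not match the five per case in the design. The futility boundary is also only a floor, and it concerns per-protocol primary-endpoint cases, whereas the 51 include superficial infections and mITT subjects. The simulations omit covariates and stepwise selection.

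**The ANCOVA contrast proves little.** Fair: titer change is the outcome there, so vaccine group is a natural predictor. Its presence does not show that leaving it out of Objective 1 was an oversight.

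**Adjusting for arm changes the question.** Objective 1 could mean the association across all trial subjects, and a vaccine-group term makes it within-arm. This is a real choice for the sponsor. It does not rescue the listed model, because the cross-arm question needs the 5:2 sampling undone.

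**Consequences are limited.** Immunogenicity is exploratory (protocol 9.3.4.1, SAP 4.2), and the Objective 2 summaries by arm and case status could expose the artefact. They would not correct the Objective 1 odds ratios.

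**Conclusion.** The concern holds. As listed, the Objective 1 model validly estimates neither the within-arm nor the cross-arm association between titer and infection. The omission and the direction of the bias follow from the documents: toward apparent protection whenever fewer than 5/7 of cases are vaccinated. The size does not follow, because it depends on the unstated case split and titer separation. If about half the cases are vaccinated and the arms differ by 1 SD or more, a null antibody effect would be reported as protective in roughly a fifth to three quarters of analyses. At a 65% share this falls to 5% to 9%. The flaw should be fixed before the analysis is run, but it does not affect efficacy or safety conclusions.

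**What to change.** In SAP 8.1.3.5 Objective 1 and Table 26, force vaccine group as a main effect into every conditional logistic model and exempt it from selection. State that its coefficient does not estimate vaccine efficacy, because sampling set the control ratio, and that the titer effect is then a within-arm association. Keep the interaction tests as secondary.

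If the association across arms is the intended estimand, specify a log inverse-sampling-fraction offset, or weights, by site and arm, and label it as a separate question. Stratifying on site by arm is an alternative but not an exact equivalent, and it may leave sparse strata.

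The cost is SAP wording and one model term, with no new subjects or assays. Using only within-arm variation widens the titer interval about 1.1-fold at 1 SD separation (SE 0.135 to 0.153), 1.4-fold at 2 SD (0.106 to 0.153) and 2.8-fold at 5 SD (0.054 to 0.153). The offset keeps the narrower interval but leaves any difference in risk between arms in the titer effect.

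### The primary serology model (SAP 8.1.3.5, Objective 1) relates infection to a Day 90 titre change that, for nearly every infection with onset by Day 90, is measured after the infection

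*SAP*

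**What the plan says.** SAP Section 8.1.3.5 replaces all earlier immunogenicity plans with a nested case-control study, written after the trial met its futility criteria. Objective 1, the primary objective, concerns the association between functional antibody levels and *S aureus* infection. On antigens it states: "The key independent variables of interest are CP5 and CP8 functional antibody levels". A conditional logistic regression models the odds of infection on "3 immunogenicity variables based on V2 and V5 described above". These are the Visit 2 admission titre, the change from admission to discharge, and "V5 post-op day 90 log transformed titers minus V2 hospital discharge log transformed titers [Quantify change from V2 discharge".

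Cases are per-protocol or mITT subjects with an adjudicated *S aureus* SSI or BSI. No limit is set on onset day. Controls are defined as follows: "Controls will be per protocol subjects from same study site as cases who completed Visit 5 (post-op Day 90", and they must be free of confirmed *S aureus* infection. On sampling: "A total of 7 controls will be selected per case (5 vaccinated and 2 unvaccinated controls per case". On strata: "Extra controls will be associated with their actual site in the logistic regression analysis".

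Visit 5 falls on Days 83-97 (Protocol 6.3.4). Efficacy onset windows are Days 1-90 or Days 1-180 (SAP 6.1), and infections are monitored to the Day 180 visit (Protocol 7.1.1). SAP Table 13 plans a Visit 5 assay for all 62 case subjects.

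The exclusion of titres taken after onset is stated for the Objective 2 time profiles. It is not in the Objective 1 text or in the Objective 1 row of Table 26. The three Objective 1 sensitivity analyses are "repeating overall model for STRIVE primary endpoints only", leaving out controls with infections due to other organisms, and restricting to per-protocol subjects.

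**The concern.** A titre drawn after an infection can be a consequence of that infection, or of its treatment. Putting it on the explanatory side of a model for the odds of infection reverses the time order. A post-infection rise pushes the odds ratio above 1 and a fall pushes it below 1, even if antibody has no bearing on risk. Controls, by design, reach Visit 5 without confirmed *S aureus* infection, so only the cases carry the shift.

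None of the sensitivity analyses removes the problem. Restricting to primary endpoints, all with onset by Day 90, concentrates the affected cases.

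The stated purpose of this work is to understand why the vaccine did not appear to prevent infection. An odds ratio that may reflect the response to infection does not answer that question.

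**Working it through.** **Plan's own figure.** 51 cases × 7 controls = 357 controls, as stated. (Tables 12 and 13 show 50 or 62 cases and 350 or 357 controls; this does not affect the point.)

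**Timing.** The earliest Visit 5 is Day 83, so onsets on Days 1-82 always precede it.
- Onset uniform over Days 1-90: 82/90 = 91.1% certainly precede Visit 5. With the visit day uniform over Days 83-97, 97.3% are expected to.
- Onset truncated exponential, scale 14 to 60 days: 95.9-99.9% certain.
- If onset can run to Day 180, the expected share before Visit 5 is 49% (uniform), 81% (exponential, scale 60) or 95% (scale 30).

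The documents do not give the onset distribution, so results are shown for a share f of cases starting before Visit 5 of 0.5, 0.7 and 1.0.

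**Expected odds ratio.** With equal spread in both groups, a mean shift of d SD gives an odds ratio per SD of exp(d). For a fold change F in a share f of cases, d is roughly f × log10(F) / SD. At f = 0.7:
- 1.25-fold: 0.7 × 0.0969 / 0.40 = 0.170 and 0.7 × 0.0969 / 0.25 = 0.271, giving odds ratios of 1.18 and 1.31. Simulated medians: 1.17-1.33.
- 1.5-fold: 0.7 × 0.1761 / 0.40 = 0.308 and 0.7 × 0.1761 / 0.25 = 0.493, giving 1.36 and 1.64. Simulated medians: 1.35-1.65.
- 0.8-fold: reciprocals of the 1.25-fold values, 0.84 and 0.76. Simulated medians: 0.76-0.85.

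**Simulated false positives for the Visit 5 term.** There is no true antibody effect, the three titre terms are fitted and vaccine group is not in the model. It was run as 51 matched sets of 1:7 and as 31 site strata with 1-4 cases each. Assumed log10 SDs are 0.6 for admission titre, 0.2 for discharge change and 0.25-0.40 for Visit 5 change. The assumed vaccine effect is 1.5 log10, and half the cases are vaccinated. Percentage of runs with p<0.05:

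| Assumed change after infection | f = 0.5 | f = 0.7 | f = 1.0 |
|---|---|---|---|
| 1.25-fold rise | 12-26 | 19-46 | 37-72 |
| 1.5-fold rise | 33-65 | 49-90 | 81-100 |
| 0.8-fold fall | 12-25 | 18-45 | 33-71 |

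With no change the rate is 4-5%. At SD 0.60 and f = 0.7 (matched sets), the three rows give 13%, 28% and 12%. Adding vaccine group moves these rates by about 1 percentage point.

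**Would the Objective 2 rule alone be enough?** No. An excluded Visit 5 value is missing, and SAP Section 7 does not impute immunogenicity values. Those cases would leave the whole three-variable model: 0.7 × 51 ≈ 36 cases if f = 0.7.

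**Is the model sound once Visit 5 is removed?** Not without vaccine group. Controls are 5/7 = 71% vaccinated by design, and vaccine group is not in the covariate lists of Objective 1 or Table 26. With no true effect, the admission term behaves as follows:

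| Share of cases vaccinated | p<0.05 without vaccine group | Median OR per log10 |
|---|---|---|
| 46% | 76-77% | 0.65-0.66 |
| 50% | 61-63% | 0.70-0.71 |
| 60% | 21% | 0.82-0.83 |
| 71% | 5% | 1.00 |

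The 46% is 11/24, the smallest vaccine share meeting the futility rule at 24 cases (SAP 8.1.1). With vaccine group in the model, the rate is 5-6% and the odds ratio 1.00 at 46-60%.

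**Discharge change.** This term has the same fault only for cases starting before the discharge sample. If 5 of 51 do (assumed; site strata, vaccine group in the model), the rate is 6% for a 1.25-fold rise and 10% for 1.5-fold, against 5.6% with no change. Excluding those 5 within their strata restores 5.6%.

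**The case against.** The strongest reply is that this is an exploratory analysis written after futility, aimed at association, with no bearing on the efficacy conclusion (SAP 4.2 defines all immunogenicity endpoints as exploratory). Objective 2 already gives pre-onset profiles and Objective 4 gives titres at infection. All of this is true and limits the severity, but neither objective corrects the Objective 1 odds ratio.

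The false-positive rates rest on assumed fold changes, spreads, onset shares and site layout. The simulation leaves out the long covariate list and the forward or backward selection, which might itself drop the Visit 5 term. Objective 1 reports odds ratios with 95% intervals and sets no significance rule. These points stand: the tables show what could happen, not the size in this trial. The time order itself does not depend on the simulation.

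Cases starting after Visit 5 are not affected, which is why f below 1 is shown.

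The vaccine-group omission is a separate fault; it matters here because it decides whether the reduced model is usable. The SAP does say "Effect modification/interaction will be tested for select variables (eg, vaccination status, colonization status, blood loss, units of transfusion", and testing an interaction would ordinarily bring in the main effect, but nothing says that it is kept. The 46% comes from per-protocol primary-endpoint cases, and the vaccine split of the broader Objective 1 case set is not given. Omitting vaccine group also means that assumed waning in vaccinees moves the Visit 5 odds ratio slightly (about 1.02-1.11 per SD) even if infection changes nothing.

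Finally, few cases may start before the discharge sample, since the protocol describes index stays as generally brief. A case infected in hospital may stay longer, however, so that number is uncertain.

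**Conclusion.** The concern holds. The Visit 5 change should not be an explanatory term in the primary Objective 1 model: for onsets on Days 1-82 it is always measured after the infection, and only onsets on Days 83-90 within the Day 90 window could follow it. The resulting bias depends on unknowns: how far infection or treatment shifts titres, in which direction, and what share of cases start before Visit 5. If there is no shift, this source of bias disappears. Under modest assumed shifts (0.8-fold to 1.5-fold, f = 0.7, SD 0.25-0.40), a null term reaches p<0.05 in about 18-90% of runs. The consequence is a primary serology result that cannot be read as protection or its absence; the vaccine efficacy conclusion is untouched. This should be fixed before the analysis is run.

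**What to change.** 1. Extend the Objective 2 rule on titres taken after onset to Objective 1 and its Table 26 row.
2. Take Visit 5 minus discharge out of the primary model. Report Visit 5 titres descriptively by case status, marking case values as before or after onset.
3. Base the primary model on the Visit 2 admission titre, with CP5 and CP8 still the key antigens. Include vaccine group as a term that selection cannot remove.
4. Fit the discharge-change term only with cases whose adjudicated onset is after the discharge sample. Drop affected cases within their site stratum, and drop their assigned controls only if individual matched sets are used. State which strata the regression uses.
5. State as a limitation that controls had to complete Visit 5.

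The cost is SAP wording, with no new assays. The Day 90 association is no longer estimated. Losing 5 of 51 cases widens the discharge-term standard error by about 5%: simulated 0.153 to 0.161 in site strata with controls kept, or √(51/46) = 1.053 if whole sets go. Under the assumed titre spread, adding vaccine group raises the admission-term standard error from 0.155 to 0.254, a factor of about 1.6.
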